3.4.1 Functional Outcomes Sleep Questionnaire (FOSQ)

3.4.1.1 Description and Rational

The FOSQ is a validated instrument that assesses the effect of a subject's daytime sleepiness on activities of ordinary living. It is a quality of life measure that is commonly used in clinical evaluation and management of OSA.

3.4.1.2 Objective and Hypotheses

The FOSQ secondary endpoint in this study will be determined by the FOSQ score at the 6-month follow-up compared with the pre-treatment Baseline. The objective is to demonstrate an improvement of daytime sleepiness measured by the FOSQ.

$$H_0: \mu_{FOSQ} \leq 0$$

$$H_A: \mu_{FOSQ} > 0,$$

where μ_{FOSQ} is the mean change of FOSQ from pre-treatment baseline to the 6-month post-treatment follow-up. This hypothesis will be tested using one-sided 95% confidence interval around the mean FOSQ.

3.4.2 Epworth Sleepiness Scale (ESS)

3.4.2.1 Description and Rationale

The ESS is a validated instrument that rates a subject's daytime sleepiness. It is a quality of life measure that is commonly used in clinical evaluation and management of OSA.

3.4.2.2 Objective and Hypotheses

The ESS secondary endpoint in this study will be determined by the ESS score at the 6-month follow-up compared with the pre-treatment Baseline. The objective is to demonstrate an improvement of daytime sleepiness measured by the ESS.

$$H_0: \mu_{ESS} \leq 0$$

$$H_A: \mu_{ESS} > 0,$$

where μ_{ESS} is the mean change of ESS from pre-treatment Baseline to the 6-month post-treatment follow-up. This hypothesis will be tested using one-sided 95% confidence interval around the mean ESS.

3.4.3 Visual Analog Scale (VAS_{snoring})

3.4.3.1 Description and Rationale

VAS is a validated instrument that rates different subjective parameters, including snoring. It is a quality of life measure that is commonly used in clinical evaluation and management of OSA. The VAS will be completed by the subject's regular bed partner.

3.4.3.2 Objective and Hypotheses

Seite 23 von 54

Protocol 990211 RAMOSA

RFA for multi-level OSA

Protocol version 6.0 from 26th September 2014

The VAS_{snoring} secondary endpoint in this study will be determined by the VAS score at the 6-month follow-up compared with the pre-treatment Baseline. The objective is to demonstrate a reduction in snoring.

$$H_0: \mu_{VAS} \geq 0$$

$$H_A: \mu_{VAS} < 0,$$

where μ_{VAS} is the mean change of VAS from pre-treatment Baseline to the 6-month post-treatment follow-up. This hypothesis will be tested using one-sided 95% confidence interval around the mean VAS_{snoring}.

3.4.4 Percentage Sleep Time at SaO₂ < 90%

3.4.4.1 Description and Rationale

The percentage of time spent with oxygen saturation below 90% has been an increasingly utilized surrogate for morbidity risk in certain sleep apnea populations.

3.4.4.2 Objective and Hypotheses

The SaO₂ secondary endpoint in this study will be determined by the SaO₂ percentage time below 90% during the 6-month PSG sleep study compared with the PSG sleep study at Baseline. The objective is to demonstrate a decrease in SaO₂ percentage time at 6-months.

$$H_0: \mu_{SaO_2\%time} \leq 0$$

$$H_A: \mu_{SaO_2\%time} > 0,$$

where $\mu_{SaO_2\%time}$ is the mean change in Percentage time with SaO₂ below 90% from Baseline to the 6-month follow-up. This hypothesis will be tested using one-sided 95% confidence interval around the mean SaO₂.

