3.4 Secondary Endpoints

Secondary endpoints will be examined to provide additional support and details of the primary endpoint findings concerning the RFA treatment. The secondary endpoints assess important patient-based clinical outcomes to compliment the biophysiological primary outcomes. It will be evaluated using mean change at 6-months follow-up from baseline. As supporting evidence, this will be tested with one-sided confidence interval with no corrections for multiple testing.

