7 INSTRUMENTS

The following outcome measures will be utilized to represent meaningful measurements of therapy success:

1. Apnea-hypopnea index (AHI) - is an index of sleep apnea severity that combines the frequency of apnea and hypopnea events. The severity of obstructive sleep apnea is determined by the measurement of apneas and hypopneas. An obstructive apnea is defined as a cessation (> 90% decrease) of airflow for at least 10 seconds with breathing effort; and a hypopnea is defined as an event with at least a 30% reduction in airflow lasting at least 10 seconds, and with $\geq 4\%$ oxygen desaturation. The frequency of apneas and hypopneas per hour of sleep is termed the apnea-hypopnea index (AHI). AHI values are typically categorized as 5–15/hr = mild; 15–30/hr = moderate; and $> 30/h$ = severe. AHI will be determined at baseline and at the 6-months follow-up visit.
2. Oxygen Desaturation Index (ODI) – ODI is defined as the number oxygen desaturation events, where there is a $\geq 4\%$ desaturation from pre-event baseline, that occur per hour of sleep. ODI generally correlates well with AHI [15], and it is reasonable to conclude that a 25% reduction in ODI represents a

Seite 34 von 54

Protocol 990211 RAMOSA

RFA for multi-level OSA

Protocol version 6.0 from 26th September 2014

clinically meaningful improvement. ODI will be determined at baseline and at the 6 months follow-up visit.

3. Epworth Sleepiness Scale (ESS) - The ESS is a validated, self-report instrument that rates a subject's tendency to fall asleep in eight common daily situations. The ESS Scale has been validated primarily in OSA. It is used to measure excessive daytime sleepiness, and is often utilized before and after the administration of treatment (e.g. CPAP) to document improvement of symptoms. The patient will complete this questionnaire at the Baseline, at Visit 3 (prior to the 1st RFA treatment), Visit 4 (prior to the 2nd RFA treatment), at Visit 5 (prior to the 3rd RFA treatment), at Visit 6 (6 weeks follow-up post 3rd RFA treatment), and at Visit 7 (6 months follow-up).

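### The one-sided alternative for percentage sleep time at SaO₂ < 90% points to an increase although the objective is a decrease; the ESS alternative appears to have the same sign error

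*Combined protocol and SAP*

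**What the plan says.** Section 3.4 (Secondary Endpoints) sets the general rule: "It will be evaluated using mean change at 6-months follow-up from baseline". It adds: "As supporting evidence, this will be tested with one-sided confidence interval with no corrections for multiple testing". The endpoint subsections then give separate hypotheses, each tested with a one-sided 95% confidence interval. None says whether the upper or the lower bound is compared with zero.

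- **Percentage sleep time at SaO₂ < 90% (3.4.4.2).** "The objective is to demonstrate a decrease in SaO₂ percentage time at 6-months". The parameter "is the mean change in Percentage time with SaO₂ below 90% from Baseline to the 6-month follow-up". The null is a mean change of zero or less, and the alternative is "H_A: \mu_{SaO_2\%time} > 0".
- **ESS (3.4.2.2).** "The objective is to demonstrate an improvement of daytime sleepiness measured by the ESS". The parameter is the mean change from pre-treatment Baseline to 6 months. The null is zero or less and the alternative is greater than zero. Section 7, item 3, says the scale rates a subject's "tendency to fall asleep in eight common daily situations".
- **Snoring VAS (3.4.3.2).** "The objective is to demonstrate a reduction in snoring". The parameter is defined in the same way, but the null is zero or more and the alternative is less than zero.
- **FOSQ (3.4.1.2).** The objective is an improvement, and the alternative is a mean change greater than zero.

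**The concern.** If change means the follow-up value minus the baseline value, a fall in desaturation time is a negative change. It then lies inside the null hypothesis of 3.4.4.2, so meeting the objective cannot support the alternative, while a rise in desaturation time can. Section 3.4.4.1 calls this measure a surrogate for morbidity risk, so the direction written as success is the unfavourable one.

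The same applies to the ESS if a higher score means a sleepier patient.

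A two-sided test would survive such a slip. A one-sided test does not, because the inequality is the only thing in the formal specification that tells a programmer which bound to compute. Section 2.3 says the clinical data will be reported to regulatory authorities. Reversing a one-sided hypothesis after the results are known would look post hoc even when the intention is plain.

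**Working it through.** **1. Sign check.** Let change = 6-month value − baseline value, as 3.4 and the from-Baseline-to-follow-up wording indicate.

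| Endpoint | Objective | Sign of change if objective met | Alternative written | Agree? |
|---|---|---|---|---|
| % time SaO₂ < 90% (3.4.4.2) | decrease | < 0 | > 0 | No |
| ESS (3.4.2.2) | improvement | < 0 if higher = sleepier | > 0 | No, on that reading |
| Snoring VAS (3.4.3.2) | reduction | < 0 | < 0 | Yes |
| FOSQ (3.4.1.2) | improvement | > 0 if higher = better function | > 0 | Yes, on that reading |

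The FOSQ scoring direction is not stated either.

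**2. Can another convention rescue the SaO₂ line?** Take change = baseline − 6 months. A decrease in desaturation time is then positive and 3.4.4.2 becomes right. A reduction in snoring is then also positive, so 3.4.3.2, which has the same parameter wording and an alternative below zero, becomes wrong. No single convention makes both lines right.

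**3. Do other sections correct it?** Section 3.3 speaks only of improvement. The section 8.2 pre/post tests compare Visit 2 with Visit 6, not with the 6-month visit. The 95% limits about the mean in section 8 are descriptive. None restates these hypotheses.

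**4. Consequence.** The plan gives no power, SD or effect size for either endpoint, so it has no figure to reproduce. The sizes below are assumed improvements *d* in units of the SD of the change. The sample sizes 43 and 48 are from section 3.2, and the one-sided 5% level follows from the one-sided 95% interval.

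For a one-sample *t* test, df = *n* − 1 and the noncentrality is *d*√*n*. For *n* = 43 the critical value is 1.682 and the noncentralities for *d* = 0.1, 0.2 and 0.5 are 0.656, 1.311 and 3.279. For *n* = 48 the critical value is 1.678.

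- Corrected direction: P(T > critical value) with noncentrality +*d*√*n*.
- Written direction: P(T > critical value) with noncentrality −*d*√*n*.

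| *n* | True improvement (SD) | Rejects as written | Rejects with sign corrected |
|---|---|---|---|
| 43 | 0.1 | 1.1% | 16% |
| 43 | 0.2 | 0.17% | 36% |
| 43 | 0.5 | below 0.0001% | 94% |
| 48 | 0.1 | 1.0% | 17% |
| 48 | 0.5 | below 0.0001% | 96% |

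By symmetry, a true *worsening* of the same size rejects the null as written with the probabilities in the last column.

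**5. Skewness.** Desaturation time may well be skewed, so the *n* = 43 case was simulated with exponential changes, 400,000 trials per setting.

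- Long tail towards improvement, *d* = 0.1, 0.2, 0.5: about 2.4%, 0.4% and no rejections as written; 11%, 32% and 99% corrected.
- Long tail towards worsening: about 0.4%, 0.06% and no rejections as written; 22%, 42% and 90% corrected.

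The figures move with the shape of the distribution, but the pattern does not.

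**The case against.** The strongest objection concerns the ESS. No section says which end of the scale is worse, and the objective says improvement without up or down. This stands as a limit on certainty: the ESS error is inferred from what the scale is said to rate, and its correction should follow confirmation of the scoring. The SaO₂ contradiction needs no such inference.

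Second, a different repair is possible. If change were defined so that positive means improvement, the SaO₂, ESS and FOSQ lines would all fit and only the snoring VAS would need reversing. That would be coherent, but it departs from the wording of 3.4 and of each parameter definition. Either way, at least one pair must change.

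Third, the impact is softened elsewhere. Section 3.3 describes the secondary analysis as descriptive, with inference in some cases, although 3.4 and its subsections say the tests will be done. Section 8.2 plans paired tests at Visit 6 and longitudinal models with no direction attached, so a fall in ESS could show up there. That does not help the SaO₂ endpoint at Visit 6, where no PSG is scheduled. These points reduce the harm without correcting the 6-month hypotheses.

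Finally, a test aimed the wrong way rarely rejects by construction, and an analyst would probably follow the prose. Both are true. The figures show what literal execution would do; they do not predict that it will happen.

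**Conclusion.** The concern holds. Section 3.4.4.2 contradicts itself: its objective lies within its own null hypothesis. The ESS pair in 3.4.2.2 has the same fault provided that a higher score means more sleepiness, which section 7 implies but does not state.

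Executed literally, neither test could be expected to show a benefit, and either could declare a worsening a success. The size of this rests on assumed standardised effects and, for the tabulated values, on approximately normal changes; the direction of the conclusion does not.

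The consequence for the trial is modest, because the endpoints are supportive and the descriptive 95% limits would reveal the true direction. It should still be corrected before the data are analysed, since a prespecified one-sided decision rule is wrong as written.

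**What to change.** 1. In 3.4, state once that change is the 6-month value minus the baseline value.
2. In 3.4.4.2, write H0: μ ≥ 0 and HA: μ < 0, and say that the objective is supported if the upper one-sided 95% confidence bound for the mean change is below 0.
3. In 3.4.2.2, add one line giving the ESS scoring direction. If higher means sleepier in the version used, make the same change of hypotheses and bound.
4. Leave the snoring VAS pair in 3.4.3.2 as it is, since it already follows this convention.

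The cost is two hypothesis pairs and two clarifying sentences. Data collection, sample size and the primary analysis do not change.

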3.5 Safety and tolerability of RFA Treatment

Safety of radiofrequency treatment will be assessed via the description of all reported adverse events. Adverse events will be summarized by seriousness, severity, relatedness to the procedure and temporal relationship to the procedure. Acute adverse events are those within 14 days of each radiofrequency treatment, long-term adverse events are those events occurring from two weeks following the final treatment until the final 6-month follow-up. No formal statistical hypotheses will be tested.

RFA specific adverse events and complications will be defined as follows (modified after Kezirian et al., 2005)⁴⁵:

- Minor: mucosal ulceration, mucosal crusting, or uvular sloughing,

- Moderate: hemorrhage that is controllable at the office, nerve paresis, or dysphagia to solid food,
- Severe: palatal fistula, hemorrhage requiring hospitalization, nerve paralysis, dysphasia requiring tube feeding, and serious infection or airway compromise requiring hospitalization or surgical intervention.

Tolerability of RFA treatment will be determined with various 100 mm VAS scales concerning pain, speech, and swallowing in order to capture patients' perceived pain, and level of speech and swallowing functions after each RFA treatment. The VAS scales will be scored by the patient immediately following each RFA procedure and 1, 3 and 7 days post-procedure. The use and amount of narcotic pain medication (hydrocodone-acetaminophen 5mg/325mg; Maximum 2 tablets every 6 hours, or 8 tablets per day; Narco®) by pill count will be recorded after each treatment. Mean score and the 95% confidence interval for the tolerability VAS scales at each RFA visit will be calculated to capture tolerability profile.

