1.5 Safety of RF ablation of the soft palate and base of tongue

Radiofrequency ablation of the soft palate and base of tongue is considered as a minimally invasive therapy with much less side effects and complications in comparison to other surgical therapies for OSAS^{39, 40}.

Potential specific complications of radiofrequency ablation include bleeding, infection, ulceration, palatal fistula, tongue weakness, and taste disturbance alongside globus sensation. Long-term complications are unusual but globus sensation may persist in up to 10 % of patients. Most patients recover quickly however and report improvements in snoring although a recent systematic review indicated that further long-term studies are required⁴¹⁻⁴³.

In a retrospective study, 130 patients underwent one to three sessions of RFA of soft palate (6 lesions) and base of tongue (6 lesions) with either Somnus (Gyros-ENT), or the CelonProSleep *plus* (Caroll et al.³², with █ the PI in this study). The most common complication of upper airway RFA was mucosal ulceration (11%; mild side effect⁴⁵), which healed with saline gargles within 10 days to 2 weeks. Ten patients (8%) had significant palatal or tongue edema (mild complication), which interfered with speech and/or swallowing but resolved within a few days of starting a taper dose of steroids. One patient had a temporary paresis of the lingual nerve (moderate complication), which resolved a couple of weeks after tongue base RFA. This was attributed to a pressure neuropathy from the laryngoscope because the lingual nerve was not within the field of the RFA application. No patient had a severe or prolonged dysphagia preventing oral diet immediately after the procedure. However, no information is given whether the complications caused by using the Somnus or the CelonProSleep *plus*³².

Factors that affect RFA complications may be repeated RFA treatment to the same tissue, learning curve of individual surgeons, energy delivered per lesion, temperature selection, anatomical site treated, and perioperative steroid use⁴⁵.

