2.4 Rational for patient selection

This study aims to evaluate the CelonProSleep *plus* for multi-level radiofrequency ablation (RFA) of the palate and base of tongue as a treatment for mild to moderate obstructive sleep apnea syndrome (OSAS) in patients with AHI of 10-30 and BMI ≤ 32 . The AHI cut-off of 30 is used because patients with AHI > 30 have OSA of such severity that they are unlikely to respond to RFA. Unlike traditional sleep surgery, RFA does not involve radical removal of tissue but works primarily by remodeling and stiffening the tissues of the upper aerodigestive tract. A meta-analysis of RFA studies found a mean AHI reduction of 45% after 24-month follow-up³⁵. Since standard measures of surgical success (AHI reduced by 50%) are applied in this study, we anticipate that many patients with severe (AHI > 30)

apnea would not be considered a surgical success and should therefore be excluded in favor of other more effective therapy for severe OSA (CPAP or traditional surgery). RFA demonstrates improved sleep outcomes if the procedure is repeated on several occasions in order to deliver enough energy to create the critical mass of scar tissue to offset the increased collapsibility of the upper airway^{32, 35}. Therefore, the present trial will repeat upper airway RFA on three occasions in order to maximize treatment effect. The treatment sessions are separated by six weeks since it takes approximately 3-4 weeks for the lesion to convert to scar and therefore all tissues should be healed by week 6³⁶. In addition, multiple studies have found that rates of surgical success for OSA decline with increasing patient BMI. This is especially true for patients with morbid obesity (BMI >40) who have a significant level of lingual and parapharyngeal fat which increase the collapsibility of the upper airway. Since most patients with OSA are overweight to obese, too low of a BMI cutoff may be overly restrictive³⁷. The BMI cut-off of 32 is a convenient rule-of-thumb frequently used by sleep surgeons which captures a large percentage of the OSA population which are more likely to succeed with sleep surgery while excluding the most obese subset who are less likely to succeed and are at increased risk for surgical complications.

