5.4 Visit 4 – Stage II: Second Radiofrequency Treatment (6 weeks later)

The study physician will perform a brief history and examination to make sure the patient tolerated the first treatment well and that the patient's tissues are fully healed with no visible ulceration or granulation. If there is a complication such as abscess and ulceration, the second treatment will be delayed until patient's tissues are fully healed. The patient will be given oral antibiotics and will then undergo a second treatment as outlined above. Treatment will be done in the same region and location since there is no concern about RFA lesion overlap once the tissues have healed. The patient will be prescribed pain medication if needed, along with a short course of oral antibiotics and steroids as outlined above.

After completion of both RFA procedures, the research team will monitor the patient for up to 3 hours post-procedure. Patients must demonstrate adequate pain control, breathing, swallowing and speech prior to discharge. The patient's vitals will be taken prior to the patient being released from the clinic. The research team will ask the patient to walk around the clinic for five minutes to assess the patient's post-operative status. The patient will be provided prescriptions for an antibiotic (amoxicillin or clindamycin), an oral steroid (7-day methylprednisolone taper pack), and an oral pain medication to take if needed (Acetaminophen/Hydrocodone). In addition, the patients will be asked to have a soft diet for at least 2 days after the treatment. The patient will then repeat the questionnaires specified above. Patients will be asked in advance to have their bed partner to drive them home. The research team will escort the patient and the bed partner out to the car as outlined above.

The patients will repeat the pain, speech, and swallowing VAS scales at 1, 3, and 7 days post RFA treatment via telephone in order to document persistent ongoing pain, and post-treatment discomfort. The amount of narcotic pain medication used in the first 7 days following the procedure will be recorded using pill count.

Medical examinations and medical actions needed due to development of side effects and/or complications will be the same as described in Section 5.3 above.

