5.5 Visit 5 - Stage III: Third Radiofrequency Treatment (6 weeks later)

The doctor will perform a brief history and examination to make sure the patient tolerated the second treatment well and that the patient's tissues are fully healed. If there is a complication such as abscess and ulceration, the third treatment will be delayed until patient's tissues are fully healed. The patient will be given oral antibiotics and will then undergo a third treatment as outlined above. Treatment will be done in the same region and location. The patient will be prescribed pain medication if needed, along with a short course of oral antibiotics and steroids as outlined above.

After completion of both RFA procedures, the research team will monitor the patient for up to 3 hours post-procedure. Patients must demonstrate adequate pain control, breathing, swallowing and speech prior to discharge. The patient's vitals will be taken prior to the patient being released from the clinic. The research team will ask the patient to walk around the clinic for five minutes to assess the patient's post-operative status. The patient will be provided prescriptions for an antibiotic (amoxicillin or clindamycin), an oral steroid (7-day methylprednisolone taper pack), and an oral pain medication to take if needed (Acetaminophen/Hydrocodone). In addition, the patients will be asked to have a soft diet for at least 2 days after the treatment. The patient will then repeat the questionnaires specified above. Patients will be asked in advance to have their bed partner drive them home. The research team will escort the patient and bed partner out to the car as outlined above.

The patients will repeat the pain, speech, and swallowing VAS scales at 1, 3, and 7 days post RFA treatment via telephone in order to document persistent ongoing pain, and post-treatment discomfort. The amount of narcotic pain medication used in the first 7 days following the procedure will be recorded.

Medical examinations and medical actions needed due to development of side effects and/or complications will be the same as described in Section 5.3 above.

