10.1.1 Adverse Event (AE)

An adverse event (AE) is any untoward medical occurrence in a subject (without taking into account the relationship with the device under investigation). The AE can be any unfavorable or unintended sign, symptom, or disease temporally associated with the use of the device (ICH E2A). All new and/or worsening adverse events (AE) will be collected throughout the study duration, starting when the subject is enrolled into the study (when the Subject Informed Consent is signed) and reported to the Sponsor on an Adverse Event Case Report Form. In addition, all deaths must be reported. Documented pre-existing conditions are not considered adverse events unless there is a change in the nature or severity of the condition and required additional medical or pharmacological treatment.

All adverse events should be followed until the adverse event has been resolved, is ongoing with no further actions to be taken, the subject exits the study or until study closure, whichever occurs first. Investigators will categorize AE's according to their severity and relatedness (e.g., to the surgical procedure, to the CelonProSleep plus, etc.). The Sponsor will then review all reported adverse events for completeness, and ask for clarification or additional information if necessary.

AE Definitions for Investigator Classification

Investigators are responsible to categorize adverse events according to their seriousness and relatedness. The definitions for classifications are included below. Those events that do not meet the criteria for Serious Adverse Event are considered non-serious.

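### The acute and long-term windows in section 3.5 leave adverse events that start between treatment sessions, after day 14, without a class in the temporal summary

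*Combined protocol and SAP*

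**What the plan says.** Section 3.5 states the planned summary: "Adverse events will be summarized by seriousness, severity, relatedness to the procedure and temporal relationship to the procedure". It then gives two timing classes. The first is "Acute adverse events are those within 14 days of each radiofrequency treatment". The second is "long-term adverse events are those events occurring from two weeks following the final treatment until the final 6-month follow-up". The first class is tied to every session, the second only to the last one. No formal safety hypothesis is tested.

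On the schedule, section 2.4 says "The treatment sessions are separated by six weeks", with three sessions in all. The interval can be longer. Section 5.4 says "If there is a complication such as abscess and ulceration, the second treatment will be delayed until" the tissue has healed, and section 5.5 has the same rule for the last session: "If there is a complication such as abscess and ulceration, the third treatment will be delayed until" healing.

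On collection, section 10.1.1 says "All new and/or worsening adverse events (AE) will be collected throughout the study duration", starting at consent. Sections 3.6 and 8.2 also plan descriptive summaries of all adverse events.

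On lasting harm, section 1.5 says "Long-term complications are unusual but globus sensation may persist in up to" 10% of patients. Section 10.4 has open events followed at each visit until closed, but lets a site close an event that is still ongoing.

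**The concern.** A summary by timing should give every post-treatment event a place. Here the acute window closes 14 days after each session, but the long-term window opens only after the third. Nothing covers the stretch from day 15 after RFA 1 or RFA 2 to the next session. No other section supplies a class; the 10-day remark in section 10.1.5.1 concerns relatedness, not timing.

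The stretch has clinical content. Section 2.4 puts conversion of the lesion to scar at about 3-4 weeks and full healing by week 6. Visits 4 and 5 begin with an examination to confirm healing. An event with onset after day 14 that is found there would have no row in the timing table. Because unhealed complications postpone the next session, the unclassified stretch is longest in patients who had one.

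At stake is a complete and reproducible description of when events occur. In a single-arm study with no safety test, the safety evidence is all descriptive, so its tables should follow rules that cover every event.

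**Working it through.** The plan states no figure for this point, so there is none to reproduce. The check assigns each day to a class.

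**Inputs**
- Acute: days 0-14 after each RFA (section 3.5).
- Long-term: from day 14 after RFA 3 to the 6-month follow-up (section 3.5).
- Sessions 42 days apart (section 2.4), so RFA falls on study days 0, 42 and 84.
- Follow-up ends 6 months after the last RFA (sections 2.5 and 5.7), taken as 182 days: study day 84 + 182 = 266.

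**Classification of days 0 to 266 (267 days)**
- Acute: days 0-14, 42-56 and 84-98, or 3 × 15 = 45 days.
- Long-term: days 98-266, or 169 days.
- In both classes: day 98 (day 14 after RFA 3), 1 day.
- In neither class: days 15-41 and 57-83, or 27 + 27 = 54 days.
- Sum: 45 + 169 − 1 + 54 = 267.

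The share unclassified is 54/267 = 20% of the whole period, and 54/84 = 64% of the time between RFA 1 and RFA 3. Day 42 itself is the day of the next session and is acute on the planned schedule.

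**Sensitivity.** For a common interval of g days the gap is 2 × (g − 15) days.

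| Assumption | Unclassified days | Share of period |
|---|---|---|
| 42-day intervals (planned) | 54 | 54/267 = 20% |
| Both sessions one week late (49 days) | 68 | 68/281 = 24% |
| Both sessions two weeks late (56 days) | 82 | 82/295 = 28% |
| 42 days, acute read as 14 days before or after an RFA | 26 | 26/267 = 10% |

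The delays are assumed for illustration; the protocol gives no expected length. The most generous reading of the acute window narrows the gap but does not close it.

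**A related loose end.** For a patient who stops after RFA 1 or RFA 2, there is a long-term window only if the final treatment means the last one received. Section 3.5 does not say.

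**The case against.** The strongest reply is that very little depends on this. Every event is collected, described overall, and classed by seriousness, severity and relatedness. A table with an unlabelled remainder row would show the unclassified events. The 20% is calendar time, not risk: section 10.1.5.1 expects procedure-related events typically within 10 days, section 5.3 schedules examinations on days 3 and 10, and section 1.3 describes necrosis by 72 hours and possible fibrosis by 10 days. Many complications that delay a session would have begun in the acute window and so already have a class. All of this stands, and it is why the point is minor. It does not remove the gap: the rule in section 3.5, followed exactly, leaves events out of a table the plan promises.

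A reader might go further and infer that section 3.5 hides lasting harm, because the long-term class does not say whether it counts events that start in the window or are present in it. Early globus still present at 6 months could then be reported as acute only. The documents do not support that as a defect of the same weight. Section 10.1.1 collects new or worsening events, so onset is the natural reading. Section 10.4 follows open events at each visit, and visual analog scales for pain, speech and swallowing are taken at Visits 6 and 7. Any figure for a hidden globus rate would need the 10% ceiling in section 1.5 to apply in full and every case to start within 14 days of a session; neither is known.

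What remains is narrower. No planned table counts patients with a related event still present at 6 months, and open/closed status cannot stand in for one because ongoing events may be closed.

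**Conclusion.** The gap is real and minor. On the planned schedule, 54 whole days per patient, about 20% of the time from RFA 1 to 6 months after RFA 3, belong to neither timing class, and more if a session is delayed. The figure assumes six-week intervals, 6 months of 182 days, and an acute window that runs forward from each session.

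A reader might infer that about a fifth of adverse events go unreported. That does not follow. No event leaves the seriousness, severity or relatedness summaries, and no study decision depends on the timing table. The number of events affected cannot be derived from the documents and may be zero. A table of persistent events is a worthwhile addition, not the correction of an error.

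**What to change.** In section 3.5, class events by onset date:
- **acute:** within 14 days of any RFA;
- **between sessions:** more than 14 days after RFA 1 or RFA 2 and before the next RFA;
- **late:** more than 14 days after the last RFA received.

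This leaves no post-treatment day unclassified, removes the one-day overlap, and covers patients who stop early.

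As a low-cost addition, because section 1.5 describes the long-term harm as persistence, report the number and percentage of patients with a related event still present at Visit 6 and at Visit 7, whatever its onset date or open/closed status. Use patients assessed at that visit as the denominator and show those not assessed separately. Dividing by the whole Safety Analysis Set would understate persistence: if 43 of 48 treated patients were seen (the plan's own dropout allowance, assumed here to fall after treatment), the percentage would shrink by a factor of 43/48 = 0.90. Visit 6 is a sensible first point: at 42 days after RFA 3 it is 28 days past the upper end of the 10-day to 2-week ulcer healing time in section 1.5, so normally healing ulcers would not be counted.

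The cost is a reworded definition, one extra table, and possibly a small check at Visits 6 and 7, where Appendix I already schedules the adverse event form. That form is not in the documents, so it may already record what is needed. The long-term rate may look less favorable.
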